In the medical literature, the term UTI has been used when bacteriuria (presence of bacteria in the urine - with or without symptoms) is present. However, for individuals living with a SCI, this classification is not appropriate as the use of urinary catheters results in colonization of the bladder with bacteria (27). Differentiating between asymptomatic bacterial colonization and a true clinical infection can also be difficult to diagnose in persons with SCI since signs and symptoms in these individuals are often subtle and not always recognized as being related to a UTI. Diagnosis has been further challenged by a lack of consensus regarding what constitutes UTI symptoms, what combination of symptoms and laboratory findings are necessary for the diagnosis, and what symptoms require antibiotic treatment (vs being managed with alternative conservative measures, such as increasing fluid intake or catheterizations) (27). Thus, the National Institute on Disability and Rehabilitation Research (NIDRR) consensus conference and the International Clinical Practice Guidelines from the Infectious Diseases Society of America (IDSA)(28) have recommended criteria for the diagnosis of significant bacteriuria in persons with SCI and catheterassociated UTI (CA-UTI), respectively.

NIDRR Guidelines: (1) $\geq 10^2$ cfu/mL (colony forming units per milliliter) for catheter specimens from individuals on intermittent catheterization; (2) $\geq 10^4$ cfu/mL for clean-void specimens from catheter-free males using condom collection devices; and (3) any detectable concentration of uropathogens from indwelling catheters or suprapubic aspirates (29). Furthermore, investigators and clinicians have categorized UTIs as being asymptomatic or symptomatic.

An asymptomatic UTI is not considered a true infection, but rather colonization of the bladder with organisms and defined by the following criteria (30):

- No symptoms and
- Initial counts of 10² cfu/ml or higher (except for indwelling catheters)
- For individuals with indwelling catheters, any detectable bacteria

A symptomatic UTI in those having neurogenic bladder is defined as (31, 32):

- Increased bacterial urine colony counts,
- Increased white blood cells in the urine (pyuria), and

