We propose to use a sample size of 36 (12 in each of the three arms). Cox et al., (46) has found that the use of intravesical gentamicin was associated with a reduction of a median 3 symptomatic UTIs in 6 months in 22 patients. Using the formulas proposed by Hozo et al., (47) we estimated the corresponding standard mean change to be 2.48 with a standard deviation of 1.7. Assuming the same standard deviation in our data, a sample size of 12 achieves 80% power to detect a mean of paired differences of as low as 1.5 symptomatic UTIs for the gentamicin group with a significance level of 0.05 using a two-sided paired ttest (48, 49). We expect to observe a drop of at least 2 symptomatic UTIs in 6 months. With the same setting, i.e. SD = 1.7, a sample size of 12 achieves 97% power to detect that. Our study will compare changes between the gentamicin instillation, the saline instillation and the no-instillation groups. We will use the comparison between the gentamicin and the non-instillation group to estimate the power. The estimated effect of gentamicin is a reduction in symptomatic UTIs of 2 with a standard deviation of 1.7 (described above) and we assume no change for the non-instillation group (mean reduction of 0 with a standard deviation of 0). With these values, sample sizes of 12 (gentamicin) and 12 (no-instillation) achieve 96% power to reject the null hypothesis of equal means with a significance level of 0.050 using a two-sided two-sample unequal-variance t-test (48-51). The power analysis was performed in PASS 14 Power Analysis and Sample Size Software (NCSS, LLC. Kaysville, Utah, USA, ncss.com/software/pass).

Experimental Outcomes – Research Procedures

1. Intravesical Gentamicin Sulfate Instillation

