University of Louisville Hospital and Frazier Rehab Institute evaluates approximately 300 chronic SCI outpatients each year. We also have a database of over 5,000 people with SCI who have expressed interest in participating in our research programs. We will select individuals to assure that there is a minimum of 25% women to adequately represent the percentage in the SCI population.

All SCI research participants, irrespective of gender, will be selected based on the following:

Inclusion Criteria

- At least 18 years of age;
- Non-progressive spinal cord injury;
- Stable medical condition;
- Bladder dysfunction as a result of spinal cord injury
- History of recurrent UTIs (defined as 3 or more within the past year or 2 or more within the past 6 months).

Exclusion Criteria

- Signs or symptoms of serious UTI that requires the use of systemic antibiotics;
- Use of any urine-acidifying agent, bladder irrigant, or systemic antibiotic within the previous 2 weeks;
- Participants colonized with gentamicin-resistant bacteria on baseline urine culture or a gentamicin allergy/sensitivity;
- Participants with known hearing loss and/or renal disease;
- Pregnant at the time of enrollment or planning to become pregnant during the time course of the study.

A. Screening and Enrollment

Potential research participants will be identified by our research database (UofL IRB 06.0647) and contacted by research staff prioritized by the initial date they entered the database and provided with general information regarding the research study. If the individual is interested in learning more about the study, the clinical coordinator will set up an info session via teleconference or a meeting at Frazier Rehab Institute. The designated project leader and clinical coordinator will attend the info session and the project leaders (Drs. [name] and [name]) will describe the project including the time commitment, the general design of the study, the interventions and the randomization process. Specific questions from the potential research participant will be answered.

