After the research participant signs the consent document, an Eligibility Checklist is completed by the research participant attesting to the eligibility requirements. This is placed in the research medical record along with supporting source documentation. These will be reviewed by the research manager and the principal investigator. The eligibility checklist will be signed by the person verifying eligibility and by the Principal Investigator who is responsible for final determination of eligibility. All source documentation for eligibility will be placed in the research medical report. We will request past medical records to determine eligibility. For research participants injured within a month of enrollment, an AIS examination would need to have been completed within four weeks of enrollment. For all other time points (three months, six months, one year, or 2 years post-injury) an AIS examination will need to be completed within three months of enrollment. If the individual has not had an AIS exam within the appropriate time point the research medical core staff will conduct the AIS exam. In consult with the medical core staff, the investigator will determine eligibility based on the medical history and the study inclusion/exclusion criteria and the research participants Attestation eligibility form. The regulatory research manager will do periodic internal audits of all enrolled research participants research medical report to ensure compliance of documentation.

C. Costs and Compensation

Participation in this study will require no additional study related costs to the research participant, unless they are injured. The participant or the participant's insurance company will be billed for all office visits, tests, medications, and procedures that are part of routine medical care outside of this research study. Participants will not be billed for the office visits, tests, medications, and procedures that are done for this research study. The charges for these items will be paid by the study. Participants will be responsible for paying co-pays associated with any office visit, test, medication, or procedure outside of this research study. Participants will be informed that some insurance companies will not pay for medical bills for individuals in research studies. It will be made clear that is the responsibility of the research participant to find out what costs, if any, the insurance company will cover before taking part in the study. The study

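### The entry criterion does not require symptomatic UTIs, and its floor does not secure the baseline rate that the expected drop of 2 symptomatic UTIs needs

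*Combined protocol and SAP*

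**What the plan says.** - **Entry (section III, Inclusion Criteria).** Participants need a "History of recurrent UTIs (defined as 3 or more within the past year or 2 or more within the past 6 months". The criterion does not use the word symptomatic and does not refer to a definition.
- **Terminology (section I.D).** The protocol notes that UTI has been used for bacteriuria with or without symptoms. It then rejects that usage in SCI, on the ground of bacterial colonization: "However, for individuals living with a SCI, this classification is not appropriate as the use of urinary catheters results in colonization of the bladder with" (final word omitted). It goes on to divide UTIs into asymptomatic and symptomatic, and describes the asymptomatic kind as colonization.
- **Outcome.** Hypothesis 1.1 concerns symptomatic UTIs. The Urine Sample Collection and Culture section requires a complaint of symptoms combined with urine findings, and does not accept smell or cloudiness alone as signs.
- **Effect and power (section II.B.2).** From a cited 22-patient series with a median reduction of 3 symptomatic UTIs in 6 months, "we estimated the corresponding standard mean change to be 2.48 with a standard deviation of 1.7". The plan then states "a sample size of 12 achieves 80% power to detect a mean of paired differences of as low as 1.5 symptomatic UTIs" and "We expect to observe a drop of at least 2 symptomatic UTIs in 6 months", and adds "SD = 1.7, a sample size of 12 achieves 97% power to detect that". For the comparison with no instillation, "we assume no change for the non-instillation group (mean reduction of 0 with a standard deviation of 0", which gives 96% power.
- **Verification (section III.B).** "an Eligibility Checklist is completed by the research participant attesting to the eligibility requirements". The same section also calls for supporting source documents, review by the research manager and principal investigator, and past medical records.

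**The concern.** Two things do not line up.

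First, entry and outcome may count different events. In catheter users, a positive culture without symptoms is what section I.D expects. If such episodes can count towards entry, some participants will start with few symptomatic UTIs to prevent. The plan also specifies paired pre-post tests in each arm. Figure 2 shows a screening phase of only 5 days, so a pre-treatment UTI rate has to come largely from history. If that history is counted loosely and follow-up strictly, every arm can show a fall that is not a treatment effect.

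Second, a person's count cannot fall by more than its starting value. The power statement rests on a mean drop of 2 in 6 months, yet the criterion admits people averaging 1.5 in 6 months, and no expected baseline links the two.

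**Working it through.** **Inputs** (section II.B.2 unless noted): n = 12 per arm; SD of change 1.7 with gentamicin and 0 with no instillation; two-sided alpha 0.05; expected drop 2; entry floors of 3 per 12 months or 2 per 6 months (section III).

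**Step 1. Reproduce the stated power.**

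Paired t-test: standard error = 1.7/√12 = 0.491, df = 11, noncentrality = drop/0.491, power from the noncentral t distribution.
- Drop 1.5: noncentrality 1.5/0.491 = 3.06, power 79.4% (plan: 80%).
- Drop 2: noncentrality 2/0.491 = 4.08, power 95.9% (plan: 97%).

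Unequal-variance two-sample test: standard error = √(1.7²/12 + 0²/12) = 0.491, Satterthwaite df = 11. With a control SD of 0 it has the same power as the paired test, so a drop of 2 gives 95.9% (plan: 96%).

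The stated figures reproduce to within two percentage points. The arithmetic of the power statement is not at issue.

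**Step 2. Put the entry floors on the 6-month scale.**
- 3 per year / 2 = 1.5 per 6 months. A drop of 2 would need a reduction of 2/1.5 = 133%, which is impossible for someone averaging that rate.
- 2 per 6 months: 2/2 = 100%, that is, complete elimination.
- For comparison, section I.B gives about 2.5 UTIs per year for SCI generally, or 1.25 per 6 months. The lower floor is only a little above that.

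**Step 3. Find the mean baseline that the expected drop needs.** Mean drop = mean symptomatic baseline × proportional reduction. A mean drop of 2 therefore needs a mean baseline of 2/1.00 = 2.0 at complete elimination, 2/0.75 = 2.67 at a 75% reduction, or 2/0.50 = 4.0 at 50%.

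**Step 4. Power at the implied drop** (n = 12 per arm, SD 1.7 against 0). The baselines and reductions are illustrative; the plan gives neither.

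| Mean baseline per 6 months | Reduction | Mean drop | Power |
|---|---|---|---|
| 2.0 | 100% | 2.0 | 95.9% |
| 2.67 | 75% | 2.0 | 95.9% |
| 4.0 | 50% | 2.0 | 95.9% |
| 1.5 | 100% | 1.5 | 79.4% |
| 2.0 | 75% | 1.5 | 79.4% |
| 2.0 | 50% | 1.0 | 46.0% |

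If the control arm also had an SD of 1.7 (my assumption), power would be 78.6%, 54.2% and 28.1% at drops of 2.0, 1.5 and 1.0.

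**Step 5. Definition shift.** Suppose the pre-value includes a episodes per participant that would not meet the on-study definition. Each arm's mean pre-post change then contains an artefact of about a. Randomization makes a similar on average in all arms, so the difference between arms keeps little of it, while each within-arm test keeps all of it. The documents give no basis for a value of a.

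**The case against.** The strongest reply is that the thresholds are floors and the drop of 2 is a group mean. The criterion admits every rate from the floor upwards, and participants with higher rates can carry the mean to 2. The plan has also discounted the source's estimated mean change from 2.48 to 2, and it reports power at 1.5. All of this stands. A reader might infer that a drop of 2 is unattainable or that enrichment fails, but the documents support neither: both would require the whole arm to sit at the floor.

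A reader might also infer from the checklist that participant attestation alone decides eligibility. Section III.B rules that out by requiring source documents, medical records and investigator review. What those records lack is a definition of a qualifying episode.

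It can further be argued that section I.D, by calling the loose use of the term inappropriate, implies that entry UTIs are clinical infections. That is a fair reading, but the criterion does not say so, and section I.D itself uses the term for asymptomatic cases.

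Finally, no section says that the eligibility history is the analysis baseline. The definition shift is therefore conditional, and it bears on the within-arm tests far more than on the comparison between arms. Nor can the dilution be quantified: the documents do not indicate what share of entrants would qualify on asymptomatic episodes.

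**Conclusion.** The concern holds in limited form, as a cheap improvement the plan should make. Entry is worded for UTIs and the outcome for symptomatic UTIs, so as written the criterion can admit people with few symptomatic events. If history supplies the pre-value, the within-arm paired results can be inflated by a change of definition.

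Separately, the floor does not secure the expected effect. Entrants averaging 1.5 per 6 months cannot average a drop of 2, those at 2 need complete elimination, and the group mean reaches 2 only with a sufficient baseline that the plan does not state. The size on the plan's own assumptions is 95.9% power at a mean drop of 2 against 79.4% at 1.5.

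These figures keep SD at 1.7. A smaller SD at low baselines would raise power, while a non-zero control SD would lower it. They are also on the plan's 6-month scale. Section III.A gives an 80-day protocol, and this point does not settle how the two periods relate.

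**What to change.** 1. Reword the inclusion criterion to count symptomatic UTIs, cross-referring to the definition under Urine Sample Collection and Culture. Where colony counts are missing from the history, accept a documented symptomatic episode treated with antibiotics.
2. Apply that definition to the medical records that section III.B already requests.
3. Use the same verified count as each participant's baseline symptomatic UTI rate, and say so in the Statistical Plan.
4. In the sample-size text, state the expected baseline rate per 6 months and express the effect as a percentage reduction from it. Restate power if the implied drop is below 2.

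The cost is amendment wording and some record abstraction. Some candidates with only asymptomatic or undocumented episodes become ineligible, though the recruitment database holds over 5,000 people for 36 places. The stated power may become less favourable.

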1. Blinding Plan: This is a double-blind study whereby the investigators, research assistants, research nurse and participants will be blinded as to the drug treatment designation. Once participants have been assessed for eligibility and enrolled in the study, they will be randomized into 1 of 3 different groups. Participants randomized to either group I or II will be blinded to the intervention fantibiotic instillation in group I or placebo (saline alone) in group II]. Gentamicin sulfate will be prescribed for the research participants by the study physician or nurse practitioner and instilled under the direction of the research nurse. Thus, the participants in groups I and II will not be able to discern their assigned treatment. To ensure the double-blind, only the study physician or nurse practitioner as well as the pharmacy, all of whom are not associated with the data collection or data analysis, will be un-blinded. Note, the research nurse assisting participants with the instillation will be blinded. All participants will be identified by number and the instillation solutions (gentamicin or placebo) will be numbered with the pharmacy having access to the code specifying which instillations are active and which are placebo for each participant. The investigators and direct research team members will not be permitted to have knowledge of the group assignments. In the case of a drug related adverse event, the study physicians will evaluate the event and prescribe treatment that will minimize or completely resolve the event if minor or moderate in severity and it does not interfere with activities of daily living or quality of life (as determined by the participant). Should it be determined that the event has gotten worse, or if the participant can no longer tolerate the event, the study drug will be discontinued, and the participant will be terminated from study participation. There are no expected reasons to unmask the study treatment. The study physician or nurse practitioner will decide if the blind is to be broken or not. The blind will not "routinely" be broken when a serious adverse event (SAE) occurs. If an SAE is probably or definitely drug-related, the drug/placebo intervention will be stopped, and the participant treated appropriately. Emergency drug code envelopes will be created by the pharmacy at the study site. These will be labeled by participant randomization number and contain information, which will un-blind the treatment of the individual subject. These envelopes are to be used only in extreme emergencies, such as when an emergency situation exists in which the participant's treatment would be affected by knowledge of his drug therapy, and there is no time to contact the Medical Monitor. Note, that at the end of the study, participants will be un-blinded to the intervention designation by the study physician or nurse practitioner. If a participant was randomized to the no instillation group, however, he/she may re-enroll into the study and directly receive the gentamicin intervention and are not required to wait until the end of study, as all parties are un-blinded and aware of the treatment (standard of care) in this instance. All data from participants re-enrolling into the gentamicin-only group will be kept separate from those who are enrolled in the main study who are blinded.

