
The following participant withdrawal criteria may be implemented in determining when and how to withdraw participants from the trial/investigational product treatment.

Drug Discontinuation Criteria:

The subject's participation may be terminated for safety precautions based on any of the following by the study investigator. 1) Drug-related severe adverse event; 2) UTI requiring intravenous antibiotics; 3) Diagnosis of systemic absorption; 4) Diagnosis of nephrotoxicity; 5) Diagnosis of ototoxicity; 6) Diagnosis of renal failure

Temporary Discontinuation Criteria:

Situations of temporary discontinuation of study drug followed by subsequent resumption of study drug are: 1) Resolution of an adverse event, especially in cases where it is determined that the study drug was unlikely to have caused the event. 2) Resolution of a symptomatic UTI.

Withdrawal from Study:

A participant may withdraw from study participation at any time. Whatever data has been collected at the time of study termination will be evaluated by the PI for use in the final study database. If a participant is terminated from the study, the investigator will have the option to recruit an additional participant. Of withdraw from the study was due to an adverse event, participants will be followed until complete resolution of the adverse event that was possibly or definitely drug-related.

2. Statistical Plan: Data will first be summarized. We will use means with associated standard deviation, median with associated interquartile range and full range (min-max) to summarize continuous variables. Categorical variables will be summarized with frequency count and standard deviation. We will perform 2 types of analyses: pre-post differences within each group and between group comparisons of the differences. To evaluate the pre-post changes in each group, we will use paired t-test. To compare the changes between the 3 groups, we will use ANOVA test. If the ANOVA test yields significant results, we will perform follow-up 2 by 2 group comparisons using 2-sample t-tests. If the underlying assumptions of these tests are not satisfied, we will use the non-parametric equivalent tests instead.

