A medical event is defined within our program as any untoward or unfavorable medical occurrence in a human research participant that occurs during the enrollment period of a study. All medical events for study participants will be recorded in a log for tracking and reporting, as the team is made aware of them. Medical events that occur during a research visit will be reported to the study nurse and then elevated to the study physician if not immediately resolved. The physician will evaluate these medical events, to determine causality with relation to the research and referral for medical care. A weekly report of all medical events is generated by the research nurse and sent to the study physician (and physician assistant), the principal investigator, the regulatory core, and the study physical therapists for review of causality and follow-up. We have developed a table outlining the most common expected events in our SCI population. These events occur with this population on a daily basis. This table will allow the IRB and our staff to understand how expected and unrelated events will be documented and reported. If a physician outside the study team treats the medical event, the study physician will follow the event to assess the following:

- The medical condition affecting their medical eligibility for research
- Determination on causality of the event
- The event's effect on research assessments or training paradigms

All conclusions reached by the study physician will be reported to the PI. If another physician treats the medical issue the study physician will follow the individual to only assess whether the medical condition affects their medical eligibility in the study or any of the research assessments or training paradigms and will notify the principal investigator. These non-study related medical events are followed by the research team and will be reported to the IRB as outlined in Medical Reporting Table. A weekly report of all medical events is generated by the research nurse and sent to the study physician (and physician assistant), the principal investigator, and the study physical therapists. In this study, a medical event will only be reported if it occurs on the same day that the assessment associated with this study also occurs.

5. Data Safety and Monitoring Plan

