Day-to-day oversight of the trial is provided by the Principal Investigators (PIs), Drs. [name] and [name]. They will review all study data and any adverse events, and report all adverse events to the Medical Monitor, sponsor, and University of Louisville IRB. Monitoring for the study will be provided by a Medical Monitor who will review study conduct including accrual, drop-outs, protocol deviations, and AEs in aggregate on an annual basis. The Medical Monitor will review serious adverse events (SAEs) in real-time. All data analyses (Labs, urodynamics, ultrasound) will be conducted as assessed with annual summary reports generated. Study data will be provided to the Medical Monitor to each annual review

one month prior. Data reports will be prepared by the principal investigators and the study statistician. The Medical Monitor will provide a written report to the study team with recommendations for study modification, study continuation/discontinuation as relevant. The study team is responsible for forwarding the report to the IRB.

Figure 2. Study Timeline.

Screening Phase		Intervention		Midpoint		Intervention			Post Intervention		
Assessments		Groups		Assessments		Groups			Assessments		
Labs	*Fxnl	Gent (n=12)	Saline (n=12)	None (n=12)	Labs	*Fxnl	Gent (n=12)	Saline (n=12)	None (n=12)	Labs	*Fxnl
UA Culture + Sensitivity	UDS US ~Intake forms	IC (n=6) 28.8 mg in 60 ml NS	IC (n=6) 60 ml NS	IC (n=6) No procedure	UA Culture + Sensitivity CBC CMP HCG	UDS US ~Intake forms	IC (n=6) 28.8 mg in 60 ml NS	IC (n=6) 60 ml NS	IC (n=6) No procedure SP (n=6) Catheter clamping for duration of instillation.	UA Culture + Sensitivity	UDS US ~Intake forms
CBC CMP HCG		SP (n=6) 28.8 mg in 60 ml NS	SP (n=6) 60 ml NS	SP (n=6) Catheter clamping for duration of instillation			SP (n=6) 28.8 mg in 60 ml NS	SP (n=6) 60 ml NS		CBC CMP HCG	
5 days		80 instillations - 7x/wk - 2x/d		5 days		80 instillations 7x/week – 2/d			5 days		

CBC, Complete Blood Count; CMP, Comprehensive Metabolic Panel; Gent, Gentamicin sulfate; IC, Intermittent Catheterization; Fxnl, Functional; HCG, Human Chorionic Gonadotropin (Pregnancy Test); NS, Normal Saline; SP, Suprapubic Catheter; UDS, Urodynamic Study; US, Ultrasound.

*The term "functional", abbreviated fxnl in this study, signifies an objective assessment of bladder functioning using urodynamic testing and ultrasound imaging.

IV. References

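### An unblinded study physician judges whether adverse events are related, so the same event can be attributed and acted on differently on gentamicin and on saline

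*Combined protocol and SAP*

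**What the plan says.** All references are to the combined protocol and SAP.

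**Who is unblinded.** Section II.B.1 (Blinding Plan) blinds the investigators, research assistants, research nurse and participants. The exceptions are "only the study physician or nurse practitioner as well as the pharmacy, all of whom are not associated with the data collection or data analysis".

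**Who judges events.** The same section states: "In the case of a drug related adverse event, the study physicians will evaluate the event and prescribe treatment". Section III.E.4 (Medical Event Reporting Unrelated to the Study) adds: "The physician will evaluate these medical events, to determine causality with relation to the research and referral for medical care". It lists causality again among the things the study physician assesses when an outside physician treats the event. It also has the physician's conclusions reported to the principal investigator (PI).

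**What the judgement feeds.**
- Section II.B.1, serious adverse events (SAEs): "If an SAE is probably or definitely drug-related, the drug/placebo intervention will be stopped".
- Section II.B.1, drug-related adverse events generally: if the event worsens or becomes intolerable, the drug is discontinued and participation ends.
- Drug Discontinuation Criteria: the first of six criteria is a severe adverse event that is drug-related.
- Withdrawal from Study: after withdrawal for an adverse event, participants are "followed until complete resolution of the adverse event that was possibly or definitely drug-related".

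**Other reviews.** Under section III.E.4 a weekly report of all medical events goes to the study physician, the physician assistant, the PI, the regulatory core and the physical therapists, for review that includes causality. Under section III.E.5 (Data Safety and Monitoring Plan) the PIs have this task: "They will review all study data and any adverse events". The Medical Monitor reviews SAEs as they occur.

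**The concern.** Whether an event is drug-related is a recorded safety judgement. The reason given for unblinding the physician, that the role is separate from data collection, does not fit a role that makes this judgement.

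A physician who knows that a syringe held only saline has little basis for calling an event drug-related. One who knows that it held gentamicin has a ready explanation. Three things are at stake in the comparison of the two instillation arms, the only one that is blinded:

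- Counts of related events can differ between the arms even where the events themselves do not.
- Where the label contributes to stopping or follow-up, participants with the same event can be handled differently. That can make exposure and loss unequal in arms of 12.
- A drug-related conclusion from someone who knows the code, once passed to the PI, can suggest that the participant is on gentamicin.

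**Working it through.** The plan states no figure on this point, so the check is to trace the roles through the sections.

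1. **Is the role that judges causality unblinded?** Section II.B.1 unblinds the study physician or nurse practitioner. Sections II.B.1 and III.E.4 give event evaluation and causality to the study physician or physicians. On the plain reading the answer is yes. The wording is not tight: the unblinding clause is in the singular and offers an alternative (physician or nurse practitioner), while the evaluation clause is in the plural. The same section has that role decide whether to break the blind and provides emergency code envelopes, which fits poorly with someone who already knows the code.

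2. **Is it causality to the drug?** Section II.B.1 speaks of drug-related events. The sentence in section III.E.4 speaks of causality to the research, under a heading on unrelated events. The stronger basis is therefore section II.B.1 read with the discontinuation and withdrawal rules; section III.E.4 confirms who does the judging and where the conclusion goes.

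3. **Does the judgement lead to action?** For SAEs, section II.B.1 makes stopping follow from the grade but does not name who assigns it. The Drug Discontinuation Criteria use drug-relatedness in criterion 1 only. Termination there is permitted rather than required and belongs to the investigator, who is blinded but is sent the physician's conclusions. Follow-up to resolution after withdrawal also uses the grade.

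4. **Does any section reserve attribution to a blinded assessor, or require it to be recorded without knowledge of the allocation?** None does. The blinded PI takes part in the weekly review but also receives the unblinded conclusion, and no order between the two is set. The Medical Monitor's blinding status and authority over attribution are not stated.

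5. **Is the assignment of the task consistent?** Section III.E.4 says both that the study physician determines causality for events treated elsewhere and, further on, that for such events the physician follows only eligibility and effects on assessments or training. The levels of relatedness also differ between rules: the SAE rule names probable or definite, and the follow-up rule possible or definite.

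6. **Can the size be computed?** If the same event occurs in both instillation arms, the expected excess of labelled events on gentamicin is

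 12 × (event rate) × (probability of labelling on gentamicin − probability of labelling on saline).

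 The documents give 12 per arm, but neither labelling probability and no event rate common to gentamicin and saline. No figure follows.

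**The case against.** The case on the other side has four parts.

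- **The link from label to stopping is partly inferred.** The SAE rule names no grader and its wording covers placebo as well as drug. Termination under the discontinuation list lies with a blinded investigator. Criteria 2 to 6 do not use relatedness, and resumption after a pause is not confined to events judged unlikely to be drug-caused. All of this stands, and it limits the conclusion to what can happen.
- **There are already checks.** The weekly causality review, the PIs' review of adverse events and the Medical Monitor's SAE review all exist. They stand as partial checks, for the reasons given in step 4.
- **The analysis may be little affected.** Section II.B.2 (Statistical Plan) plans no test of related-event counts, and its between-group power calculation uses gentamicin against no instillation, which is open. This stands. Gentamicin against saline is still one of the follow-up comparisons after a significant ANOVA, so unequal stopping could reach it. The option to recruit a replacement for a terminated participant restores numbers but not the original randomised group.
- **A saline event can be called related to the research.** It can, because research includes instillation and assessments. But the rules on stopping and follow-up speak of the drug.

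A reader might go further and size the bias from section III.D.1 (Potential Risks), where local allergic reaction and opportunistic infection are listed as less likely, defined as 11-30%. That would give 12 × 0.11 = 1.3 to 12 × 0.30 = 3.6 labelled participants on gentamicin against none on saline. The documents do not support this. Those entries describe reactions to gentamicin, so a higher count on gentamicin could be correct attribution. The sum also assumes every event is labelled in one arm and none in the other. Nor do labels convert to terminations, since section II.B.1 has tolerated minor or moderate events treated rather than ended.

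**Conclusion.** The concern holds as an opening for bias. The plan lets an unblinded role judge relatedness, lets that judgement feed stopping, one discontinuation criterion and follow-up, and passes it to a blinded PI. The same event can therefore be attributed and acted on differently in the two instillation arms, and the conclusion itself can hint at the assignment.

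The size is unknown and cannot be derived from the documents. A reader might infer that related-event counts must be biased against gentamicin, or that a drug-related label can be given only on gentamicin. Neither follows: the SAE grader is not named, the rule as worded covers placebo, and blinded roles also see the events.

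The conclusion rests on two assumptions: that the study physician who evaluates events is the one unblinded in section II.B.1, and that no separate procedure outside these documents blinds the attribution. It concerns gentamicin against saline only, since the no-instillation arm is open by design.

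**What to change.** For the two instillation arms:

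- Have a blinded role already in the plan record relatedness. This can be the PIs, through the existing weekly causality review, or the Medical Monitor if that role is confirmed to be blinded. The record is made from an event report without the treatment code and before the unblinded physician's conclusion is seen.
- Use that record for safety reporting by arm, and report all adverse events by arm regardless of attribution. The log of medical events in section III.E.4 is a natural source.
- Leave the unblinded physician free to treat and to act for safety. Record any stop made on unblinded knowledge as such.
- State the Medical Monitor's blinding status.

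Leave the clinical stopping criteria unchanged. Rewording them to refer to the instillation instead of the drug would alter a clinical trigger, and it would meet the separate rule in section III.E.3 (Interventions) for SAEs resulting from instillation.

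Reconcile section II.B.1 (including the discontinuation and withdrawal rules), section III.E.3 and section III.E.4 on who assigns relatedness, on what scale, and whether that person is blinded.

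The cost is a short amendment and a line on the event form, with no new staff. The downside is a small extra reporting step before relatedness is recorded.
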